**6.16 Lost-to-Follow-up (LTFU)**

If a subject misses two consecutive scheduled follow-up visits, trial personnel will make all possible attempts to contact the subject per the site’s standard of practice. If the Investigator concurs and at least two unsuccessful documented attempts on two different days have been made to contact the subject, the subject will be considered lost-to-follow-up. The date, time and name of site personnel attempting to contact the subject, along with the Investigator’s concurring opinion must be documented in the subject’s medical records. Upon determination that the subject is LTFU, a letter must be sent to the subject’s residence and a copy of the letter saved in the subject’s medical records. If a subject who has been considered LTFU is relocated and is interested in remaining in the trial, LTFU status may be revoked with documentation in the subject’s medical record along with the associated protocol deviation for missed visits. If a

	Title: The WAVECREST 2 Trial  Clinical Investigational Plan	Doc. #: CHX_IP014	Rev: H
---	--	-----------------------------	------------------

subject relocates or moves and an Investigator is located in the general area, trial records may be transferred to another site and follow-up continued.

### 6.17 Early Trial termination

The Sponsor reserves the right to terminate the clinical trial at any stage with suitable written notice to the Investigators. Possible reasons for termination are:

- Physician Advisory Committee makes a recommendation for early termination based upon input from the Data Monitoring Committee
- Unanticipated Adverse Device Effects (UADEs) present an unreasonable risk to subjects

If the trial is terminated early, the Sponsor will provide a written statement to the Investigators to enable notification to the IRB/EC or will notify the EC directly as appropriate for OUS sites. The Sponsor will also notify FDA and Competent Authorities (CAs), as applicable, of trial termination. Should the trial be terminated by the Sponsor, subjects must continue to be followed per routine hospital practice and device-related adverse events must be reported per the manufacturer’s procedures and applicable regulations.

Should early termination occur, the Investigator shall return all clinical trial materials (including investigational devices) to the Sponsor.

## 7. COMPLIANCE TO CIP

### 7.1 Statement of Compliance

This trial will be conducted in accordance/compliance with this CIP, the most current version of the World Medical Association (WMA) Declaration of Helsinki, ISO14155, and any regional and/or national regulations, as appropriate.

The sites will not start enrolling subjects or request informed consent from any subject prior to obtaining IRB/EC approval and Competent Authority approval, if applicable, execution of appropriate Investigator and/or site agreements, and authorization from the Sponsor in writing for the trial.

In case additional requirements are imposed by the IRB/EC or Competent Authority, those requirements will be followed, if appropriate. If any action is taken by an IRB/EC, and regulatory requirements with respect to the trial, that information will be forwarded to Coherex Medical.

As Sponsor, Coherex Medical has taken up general liability insurance in accordance with the requirements of the applicable local laws. Appropriate country representatives will be utilized to understand the requirements for the type of insurance that will be provided for subjects, such information will be incorporated into the informed consent, as applicable.

If required, additional subject coverage or a trial specific insurance will be provided by the Sponsor as well.

	Title: The WAVECREST 2 Trial  Clinical Investigational Plan	Doc. #: CHX_IP014	Rev: H
---	--	-----------------------------	------------------

## 7.2 Adherence to the Clinical Investigation Plan

A deviation is defined as an event where the clinical Investigator, site personnel, Sponsor or Sponsor representative did not conduct the clinical trial according to the CIP, IRB/EC requirements or the Clinical Trial Agreement. The Investigator is not allowed to deviate from the CIP, except as specified under emergency circumstances.

In some cases, failure to comply with the CIP may be considered failure to protect the rights, safety and well-being of subjects, since the non-compliance exposes subjects to unreasonable risks. For example, failure to adhere to the inclusion/exclusion criteria: these criteria are specifically defined by the Sponsor to exclude subjects for whom the device is not beneficial, and the use involves unreasonable risks. This may be considered failure to protect the rights, safety and well-being of the enrolled subject. Similarly, failure to perform safety assessments intended to detect adverse events may be considered failure to protect the rights, safety and well-being of the enrolled subject. Investigators should seek minimization of such risks by adhering to the CIP.

Simultaneously, in the event that adhering to the CIP might expose the subject to unreasonable risks, the Investigator is also required to protect the rights, safety and well-being of the subject by intentionally deviating from the requirements of the CIP, so that subjects are not exposed to unreasonable risks.

It is the responsibility of the Investigator to provide adequate medical care to a subject enrolled in a trial.

Investigators will inform their IRB/EC of protocol deviations in accordance with their specific IRB/EC reporting policies and procedures.

Regulations require that the PI maintain accurate, complete, and current records, including documents showing the date of and reason for every deviation from the CIP. Relevant information for each deviation will be documented.

Regulations require Investigators obtain approval from Coherex Medical and the IRB/EC [as required] before initiating changes in or deviations from the protocol, except when necessary to protect the life or physical well-being of a subject in an emergency. Under emergency circumstances, deviations from the CIP to protect the rights, safety and well-being of human subjects may proceed without prior approval of the Sponsor and the IRB/EC. Such deviations shall be documented and reported to the Sponsor and the IRB/EC as soon as possible, but no later than 5 working days.

Prior approval must be requested when the Investigator anticipates, contemplates, or makes a conscious decision to depart from the CIP, except when unforeseen circumstances are beyond the Investigator's control (e.g. a subject who fails to attend a scheduled follow-up visit, a subject is too ill to perform a CIP-required test, etc.). All deviations, including those beyond the Investigator's control, must be reported on a CRF.

All deviations must be reported to appropriate regulatory authorities in specified timelines (if appropriate).

	Title: The WAVECREST 2 Trial  Clinical Investigational Plan	Doc. #: CHX_IP014	Rev: H
---	--	-----------------------------	------------------

In the event an Investigator is not compliant with this CIP, regulatory requirements or the Investigator Agreement, the Investigator will be notified of the non-compliance. In the event of repeated non-compliance, the Sponsor will attempt to secure compliance by one or more of the following actions

- Visiting the Investigator
- Contacting the Investigator by telephone
- Contacting the Investigator in writing
- Retraining of the Investigator

Repeated non-compliance despite these steps may result in further escalation in accordance with the Sponsor’s procedures, including termination of the Investigator's participation in the trial.

## 8. ADVERSE EVENT, ADVERSE DEVICE EFFECTS, DEVICE DEFICIENCY

### 8.1 Definitions

#### 8.1.1 Medical Device

Any instrument, apparatus, implement, machine, appliance, implant, software, material or other similar or related article

- Intended by the manufacturer to be used, alone or in combination, for human beings for one or more of the specific purpose(s) of
  - Diagnosis, prevention, monitoring, treatments or alleviation of disease,
  - Diagnosis, monitoring, treatment, alleviation of, or compensation for, an injury,
  - Investigation, replacement, modification, or support of the anatomy or of a physiological process,
  - Supporting or sustaining life,
  - Control of conception,
  - Disinfection of medical devices and
- Which does not achieve its primary intended action in or on the human body by pharmacological, immunological or metabolic means, but which may be assisted in its intended function by such means

#### 8.1.2 Adverse Event

An adverse event is any untoward medical occurrence, unintended disease or injury, or untoward clinical signs (including abnormal laboratory findings) in subjects, users or other persons, whether or not related to the investigational device or comparator. This definition includes events related to the procedures involved.

**Note:** Unchanged, chronic, non-worsening or pre-existing conditions are not adverse events, but any planned treatment or intervention/elective procedure must be reported on the Non-AE/Planned Procedure eCRF.

The Investigator must monitor and report the occurrence of adverse events for each subject from the time of enrollment through all trial follow-up. Adverse events, including the event

	Title: The WAVECREST 2 Trial  Clinical Investigational Plan	Doc. #: CHX_IP014	Rev: H
---	--	-----------------------------	------------------

description, date of onset, outcome, whether or not any medication changed, or a hospitalization or intervention occurred, and whether the adverse event was resolved (if so, how, and date of resolution), must be reported on the appropriate eCRF within 2 weeks from when the investigator becomes aware of the event. Every effort must be made to report the underlying condition or unifying diagnosis for the event. To avoid vague, ambiguous, or colloquial expressions, adverse events must be recorded in standard medical terminology rather than the subject's words. The eCRF must be updated as additional information on the event is received. In addition to reporting requirements specified in this CIP, sites must follow the Watchman manufacturer's adverse event reporting requirements for subjects randomized to the Watchman device.

**Relatedness to Device or Procedure**

Relationship of an adverse event to the investigational device (or comparator) or the procedure will be based on assessment of temporal relationships, biologic plausibility, association (or lack of association) with underlying disease and presence (or absence) of a more-likely cause. Device or procedure relationship of each adverse event will be categorized as the following: not related, unlikely, possible, probable, or causal relationship, as adapted from MEDDEV 2.7/3:

1) Not related: relationship to the device or procedures can be excluded when:

- the event is not a known side effect of the product category the device belongs to or of similar devices and procedures;
- the event has no temporal relationship with the use of the investigational device or the procedures;
- the serious event does not follow a known response pattern to the medical device (if the response pattern is previously known) and is biologically implausible;
- the discontinuation of medical device application or the reduction of the level of activation/exposure - when clinically feasible – and reintroduction of its use (or increase of the level of activation/exposure), do not impact on the serious event;
- the event involves a body-site or an organ not expected to be affected by the device or procedure;
- the serious event can be attributed to another cause (e.g. an underlying or concurrent illness/ clinical condition, an effect of another device, drug, treatment or other risk factors);
- the event does not depend on a false result given by the investigational device used for diagnosis, when applicable;
- harms to the subject are not clearly due to use error;
- In order to establish the non-relatedness, not all the criteria listed above might be met at the same time, depending on the type of device/procedures and the serious event.

2) Unlikely: the relationship with the use of the device seems not relevant and/or the event can be reasonably explained by another cause, but additional information may be obtained.

3) Possible: the relationship with the use of the investigational device is weak but cannot be ruled out completely. Alternative causes are also possible (e.g. an underlying or concurrent illness/

	Title: The WAVECREST 2 Trial  Clinical Investigational Plan	Doc. #: CHX_IP014	Rev: H
---	--	-----------------------------	------------------

clinical condition or/and an effect of another device, drug or treatment). Cases where relatedness cannot be assessed, or no information has been obtained should also be classified as possible.

4) Probable the relationship with the use of the investigational device seems relevant and/or the event cannot be reasonably explained by another cause, but additional information may be obtained.

5) Causal relationship: the serious event is associated with the investigational device or with procedures beyond reasonable doubt when:

- the event is a known side effect of the product category the device belongs to or of similar devices and procedures;
- the event has a temporal relationship with investigational device use/application or procedures;
- the event involves a body-site or organ that
  - the investigational device or procedures are applied to;
  - the investigational device or procedures have an effect on;
  - the serious event follows a known response pattern to the medical device (if the response pattern is previously known);
  - the discontinuation of medical device application (or reduction of the level of activation/exposure) and reintroduction of its use (or increase of the level of activation/exposure), impact on the serious event (when clinically feasible);
  - other possible causes (e.g. an underlying or concurrent illness/ clinical condition or/and an effect of another device, drug or treatment) have been adequately ruled out;
  - harm to the subject is due to error in use;

The investigator will distinguish between adverse events related to the investigational device and those related to the implant procedure. An adverse event can be related both to the implant procedure and the investigational device.

In some particular cases the event may be not adequately assessed because information is insufficient or contradictory and/or the data cannot be verified or supplemented. The investigator will make the maximum effort to define and categorize the event and avoid these situations.

Where the investigator remains uncertain about classifying the event, it should not exclude the relatedness and classify the event as “possible”.

### 8.1.3 Serious Adverse Event

An adverse event that led to:

- Death,
- A serious deterioration in health of the subject, that either resulted in:
  - A life-threatening illness or injury, or
  - A permanent impairment of a body structure or a body function, or
  - An inpatient hospitalization or prolongation of existing hospitalization, or

	Title: The WAVECREST 2 Trial  Clinical Investigational Plan	Doc. #: CHX_IP014	Rev: H
---	--	-----------------------------	------------------

- A medical or surgical intervention to prevent life-threatening illness or injury or permanent impairment to a body structure or a body function
- Fetal distress, fetal death or a congenital abnormality or birth defect

**Note:** A planned hospitalization or treatment/elective procedure for a pre-existing condition, or a procedure required by this Clinical Investigation Plan, without serious deterioration in health, is not considered a serious adverse event (e.g., non-emergent cardioversion), but must be reported on the Non-AE/Planned Procedure eCRF.

SAEs must be reported to the Sponsor as soon as possible but no longer than 72 hours (or within the timeline specified by site’s local IRB/EC requirements, if these requirements are more stringent) on the appropriate eCRF from the time trial personnel became aware of the event or became aware that the event met the definition of a serious adverse event. In the event that the eCRF database is not available, the Investigator must report the SAE to the Sponsor via email. The SAE must then be entered as soon as possible in the eCRF. The Investigator must report the SAE to the local IRB/EC according to the IRB/EC reporting requirements.

**8.1.4 Adverse Device Effect (ADE)**

Adverse event related to the use of an investigational medical device. ADEs must be reported on the appropriate eCRF (AE eCRF) within 2 weeks from when the Investigator becomes aware of the event.

NOTE 1- This includes any adverse event resulting from insufficiencies or inadequacies in the instructions for use, the deployment, the implantation, the installation, the operation, or any malfunction of the investigational medical device.

NOTE 2- This includes any event that is a result of a use error or intentional misuse.

**8.1.5 Unanticipated Serious Adverse Device Effect (USADE)**

A serious adverse device effect which by its nature, incidence, severity or outcome has not been identified in the current version of the risk analysis report. A USADE must be reported as soon as possible but no longer than 72 hours after becoming aware of the event, on the eCRF.

**8.1.6 Unanticipated Adverse Device Effect (UADE)**

As defined in 21 CFR §812.3, unanticipated adverse device effects (UADE) are defined as any serious adverse effect on health or safety or any life-threatening problem or death caused by, or associated with, a device, if that effect, problem, or death was not previously identified in nature, severity, or degree of incidence in the CIP or application (including a supplementary plan or application), or any other unanticipated serious problem associated with a device that relates to the rights, safety, or welfare of subjects.

If an unanticipated adverse device effect occurs, the Investigator must notify Coherex Medical as soon as possible but no longer than 72 hours of the Investigator becoming aware of the event on the eCRF. The Sponsor will notify all IRBs/ECs and all Investigators within 10 working days of the Sponsor’s knowledge of the event, as required by 21 CFR §812.150. Coherex Medical will

	Title: The WAVECREST 2 Trial  Clinical Investigational Plan	Doc. #: CHX_IP014	Rev: H
---	--	-----------------------------	------------------

take any steps necessary to investigate the event and will be responsible for notifying FDA and all other participating IRBs/ECs, CAs, as appropriate, and Investigators.

**8.1.7 Anticipated Serious Adverse Device Effect (ASADE)**

A serious adverse device effect which by its nature, incidence, severity or outcome has been previously identified in the risk analysis report. Such events must be reported on the eCRF no longer than within 72 hours of awareness of the event.

**8.2 Procedure for assessing, recording and reporting adverse events, device deficiencies/complaints, adverse device effects, serious adverse events and serious adverse device effects:**

Safety surveillance within this trial and the safety reporting both performed by the Investigator, starts as soon as the subject is enrolled in this trial (date of signature of the informed consent). The safety surveillance and the safety reporting will continue until the last investigational visit has been performed, the subject is deceased, the subject/Investigator concludes his/her participation in the trial, or the subject/Investigator withdraws the subject from the trial, except as otherwise specified in the CIP.

All adverse event data including deaths and device deficiency data (if applicable) will be collected throughout the clinical trial and will be reported to the Sponsor through the EDC system.

Records relating to the subject’s subsequent medical course must be maintained and submitted (as applicable) to the Sponsor until the event has subsided or, in case of permanent impairment, until the event stabilizes, and the overall clinical outcome has been ascertained. Adverse events will be monitored until they are adequately resolved. The status of the subject’s condition should be documented at each visit.

Reportable events to the Sponsor are considered:

- All Adverse Device Effects
- All Serious Adverse Events (whether or not the event is considered device- or procedure-related and regardless the randomization group)
- (if applicable) device deficiencies, that could have led to a serious adverse device effect
  - if either suitable action had not been taken;
  - if intervention had not been made or
  - if circumstances had been less fortunate

All above events will be reported to the Sponsor, as soon as possible, but no later than 72 hours of first learning of the event.

The Sponsor will ensure that all events and device deficiencies are reported to the relevant authorities as per regulations.

Additional information may be requested, when required, by the Sponsor or CEC in order to support the reporting of AEs to regulatory authorities.

	Title: The WAVECREST 2 Trial  Clinical Investigational Plan	Doc. #: CHX_IP014	Rev: H
---	--	-----------------------------	------------------

The Investigator must notify the IRB/EC, if appropriate, in accordance with national and local laws and regulations, of the AEs reported to the Sponsor.

### 8.3 Subject Death

Subject deaths must be reported as soon as possible but no later than 24 hours (or within the timeline specified by site’s local IRB/EC requirements, if these requirements are more stringent) on the appropriate eCRF from the day trial personnel become aware of the event. Upon subject death, a trial completion eCRF must also be completed. Deaths will be reported as cardiovascular or non-cardiovascular (**Appendix I: Acronyms and Definitions**). In the event that the eCRF database is not available the Investigator must report the SAE to the Sponsor in a timely fashion via email. The death must then be entered as soon as possible in the eCRF once the eCRF database becomes available. The Investigator must report the death to the local IRB/EC according to the IRB/EC reporting requirements. In the event of subject death within 45 days of the implant procedure, an autopsy should be ordered, and the autopsy report submitted to the Sponsor.

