**18.2 Clinical Event Committee (CEC)**

A Clinical Events Committee (CEC) composed of physicians from different specialties will be appointed by the Sponsor to adjudicate primary effectiveness and safety endpoints, secondary endpoints, death (cardiovascular vs. non-cardiovascular), and bleeding categories. CEC members will not be on the Physician Advisory Committee or Investigators in the trial. The CEC will be composed of at least 4 physicians: 2 stroke Neurologists and 2 Cardiologists. Each CEC meeting will require a quorum. The names of the CEC members, responsibilities of the CEC, the frequency of CEC meetings, the adjudication process and the process for documentation of the adjudication outcome will be specified in a **CEC Charter**. CEC members will be blinded to subject’s randomization assignment and implanted device.

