Procedural Success	
 
• Technical success
 
• No procedure-related complications except uncomplicated (minor) device embolization (resolved by percutaneous retrieval during the procedure without surgical intervention or damage to surrounding cardiovascular structures)
 

Device Success	
 
• Device deployed and implanted in the correct position
 

Death	VARC II Definition 
Cardiovascular Death	Death that meets any of the following criteria: 
 
• Death due to proximate cardiac cause (e.g., myocardial infarction, cardiac tamponade, worsening heart failure)
 
• Death caused by non-coronary vascular conditions such as neurological events, pulmonary embolism, ruptured aortic aneurysm, dissecting aneurysm, or other vascular disease
 
• Procedure-related death, including death related to complication of the procedure or treatment for a complication of the procedure
 
• Valve-related death including structural or non-structural valve dysfunction or other valve-related adverse events
 
• Sudden or unwitnessed death
 
• Death of unknown cause
 

Non-cardiovascular Death	Death in which the primary cause of death is clearly related to another condition (e.g., trauma, cancer, suicide)
Endocarditis	Fulfillment of the Duke endocarditis criteria  (see http://www.medcalc.com/endocarditis.html )
LAA Closure	No residual leak or if leak is present, residual gap ≤ 5mm (assessed by the ECL)
Major Bleeding	Bleeding Academic Research Consortium (BARC)  definition
Type 3a	Overt bleeding plus hemoglobin drop of 3 to < 5g/dL* (provided hemoglobin drop is related to bleed) Any transfusion with overt bleeding

	Title: The WAVECREST 2 Trial  Clinical Investigational Plan	Doc. #: CHX_IP014	Rev: H
---	--	-----------------------------	------------------

Type 3b	Overt bleeding plus hemoglobin drop $\geq 5\text{g/dL}^*$ (provided hemoglobin drop is related to bleed) Cardiac tamponade Bleeding requiring surgical intervention for control (excluding dental/nasal/skin/hemorrhoid) Bleeding requiring intravenous vasoactive agents

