Residual Gap	Space between the implanted device and adjacent LAA tissue. This gap is measured on TEE where there is high velocity color flow and a 2d image showing space between implant and tissue.
Roll-In	WaveCrest subjects enrolled prior to a site’s randomization phase who had vascular access attempted
Stroke/TIA All Stroke	Any ischemic, hemorrhagic, or indeterminate stroke

	Title: The WAVECREST 2 Trial  Clinical Investigational Plan	Doc. #: CHX_IP014	Rev: H
---	--	-----------------------------	------------------

Ischemic Stroke	Sudden onset neurological deficit in a vascular territory thought to be due to cerebral or retinal ischemia that a) lasts longer than 24 hours or b) lasts less than 24 hours and is associated with a neuroanatomically relevant lesion on neuroimaging or confirmed visualized retinal infarct. A global (rather than focal) deficit thought to be due to anoxic brain injury is not considered a stroke. Ischemic stroke with hemorrhagic transformation is also categorized here.
Hemorrhagic Stroke	Any symptomatic intracerebral or subarachnoid hemorrhage.
TIA	Sudden onset neurological deficit in a vascular territory thought to be due to cerebral or retinal ischemia with resolution in less than 24 hours and without evidence of tissue injury on imaging or fundoscopic examination
Major Stroke	
 
Any change on the mRS score > 2 points that persists at 90 days post-stroke
 

Minor Stroke	
 
Stroke symptoms which last longer than 24 hours with evidence of tissue injury but which does not meet definition of Major Stroke
 

Stroke of Cardioembolic Origin	Using ASCOD Classification system  Stroke will be considered cardioembolic except if there is: 
 
Another “potentially causal” mechanism is identified (any of A1, S1, O1, D1)
 

Systemic Thromboembolism	Any peripheral ischemic event evidenced by ischemic tissue or radiologic imaging evidence of perfusion deficit

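### The ischemic stroke definition has no limb for a deficit ended by death within 24 hours, so an early fatal stroke without imaging evidence falls outside the primary effectiveness endpoint

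*Protocol*

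**What the plan says.** The primary effectiveness endpoint is ischemic stroke or systemic embolism at 24 months (protocol 4.3.1 and 15.4). It has no death component.

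Appendix I defines ischemic stroke as a sudden deficit, thought to be ischemic, that "a) lasts longer than 24 hours or b) lasts less than 24 hours and is associated with a neuroanatomically relevant lesion on neuroimaging"; a confirmed retinal infarct also satisfies limb (b). Neither limb mentions death or autopsy. TIA requires resolution within 24 hours.

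On deaths, section 8.3 says "Deaths will be reported as cardiovascular or non-cardiovascular". Under 18.2 the CEC is to "adjudicate primary effectiveness and safety endpoints, secondary endpoints, death (cardiovascular vs. non-cardiovascular), and bleeding categories". The cardiovascular class in Appendix I includes "Death caused by non-coronary vascular conditions such as neurological events, pulmonary embolism" and "Sudden or unwitnessed death", with no separate class for stroke death. All-cause death is part of the primary safety endpoint.

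**The concern.** The definition sorts deficits by how long they last, and death can cut that duration short. A stroke that kills within hours may therefore fail the duration test because it was so severe. If there is also no lesion on a scan, no category fits: it is neither an ischemic stroke nor a TIA.

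The device is meant to prevent ischemic stroke, and some of the most severe strokes could then count only on the safety side, pooled with unrelated deaths and major bleeding. In a non-inferiority comparison against a ratio margin of 1.75, lost events mean lost information.

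**Working it through.** **Reading the definitions against one case.** Take a subject with a sudden focal deficit thought to be ischemic who dies 10 hours after onset.

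- Limb (a): the deficit lasted 10 hours, not more than 24. Not met.
- Limb (b), scan shows a relevant lesion: met, and the event counts.
- Limb (b), no scan or a negative scan, and no retinal infarct: not met.
- TIA: nothing resolved. Not met.
- Systemic thromboembolism: this definition has no duration test, so it does not share the gap, but it covers peripheral events only.

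The gap is therefore death within 24 hours of onset and no imaging or retinal evidence.

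**Comparison within Appendix I.** The myocardial infarction definition provides for death before biomarkers could be drawn. The bleeding scale has a fatal category and accepts autopsy confirmation for intracranial hemorrhage. Hemorrhagic stroke has no duration test. Ischemic stroke alone among these has no provision for death or autopsy, which reads as an omission.

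**Size.** The plan gives no figure for this point, so there is none to reproduce. Inputs:

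- Subjects per arm: 1550/2 = 775 at the maximum size (SAP 8.5).
- Event rate: 0.0253 for ischemic stroke or systemic embolism in the device arm of the second earlier Watchman trial (protocol 2.6). The text is unclear whether this is an 18-month risk or a rate per subject-year, so both readings are used.
- Share of events lost: 2%, 5% or 10%. This is an assumption; the documents give no figure.

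As an 18-month risk under constant hazard: 1 − (1 − 0.0253)^(24/18) = 3.36%, and 775 × 0.0336 = 26.0 events.
As a rate per subject-year: 1 − exp(−2 × 0.0253) = 4.93%, and 775 × 0.0493 = 38.2 events.

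| Reading of 0.0253 | Events per arm | 2% lost | 5% lost | 10% lost |
|---|---|---|---|---|
| 18-month risk | 26.0 | 0.5 | 1.3 | 2.6 |
| Per subject-year | 38.2 | 0.8 | 1.9 | 3.8 |

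At the minimum size (1250/2 = 625 per arm) the events are 21.0 and 30.8, and the loss runs from 0.4 to 3.1 per arm.

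**Precision.** The standard error of a log ratio varies roughly as 1/√events. With equal loss in both arms it grows by 1/√0.98 = 1.010 to 1/√0.90 = 1.054, that is, by about 1-5%. In a simple fixed-design approximation (margin 1.75, true ratio 1, assumed one-sided alpha 0.025 or 0.05), power falls by about 1 to 5 points. This does not test the plan's stated power, because its Bayesian adaptive design is redacted.

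**The case against.** The strongest reply is that the adjudication system would catch these cases. Much of that stands.

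- **The death classes exclude nothing.** A reader might infer from 8.3 that a fatal stroke is filed as a cardiovascular death and goes no further. Section 18.2 lists primary effectiveness events and class of death as separate CEC tasks, so one event can be both.
- **Cause of death is sought.** A reader might infer that nobody asks whether a death was a stroke, or that the neurology work-up in 6.12 is the only way such a case comes to light. But 6.15 requires the cause of death to be documented, 8.1.2 asks sites to report the underlying diagnosis, 8.1.3 and 8.2 make every fatal event reportable, and the CEC may request more information. None of this needs a living subject. The CEC also has at least two stroke neurologists.
- **A rule may exist elsewhere.** The adjudication process is in the CEC Charter, which was not provided, and SAP 8.3 is largely redacted.
- **Fatal strokes still count against the device.** All-cause death is in the primary safety endpoint, and trial success needs both primary endpoints (protocol 15.8).

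What this does not answer is the wording. A committee that finds every such death must still apply the visible definition, and that definition leaves the case out. A count in safety is not a count in effectiveness.

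**Conclusion.** The gap is real but narrow. Read literally, Appendix I leaves out an ischemic stroke that kills within 24 hours without an imaging lesion or retinal infarct. The likely loss is about 0.5-4 events per arm at 775 per arm, with about 1-5% of precision if the loss is equal. Those figures rest on the assumed 2-10% share and on an ambiguously worded historical rate. They also assume that no rule in the CEC Charter or the redacted SAP text already covers the case.

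Two stronger readings are not supported. First, a reader might infer that the effectiveness ratio rests only on survivors and slower deaths. It does not, because early deaths with an imaging lesion count. Second, a reader might infer a material bias: three more events lost in one arm would be 3/38.2 = 8% to 3/26.0 = 12% of that arm's events. At 26.0 events the largest assumed loss is 2.6, so a difference of three cannot arise. At 38.2 events it needs about 10% loss in one arm (3.8) and 2% in the other (0.8). The arms do follow different antithrombotic regimens, but the documents show no mechanism for unequal loss: one definition applies to both arms and the CEC is blinded.

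**What to change.** 1. In Appendix I, add *or until death* after the 24-hour criterion in limb (a). The opening requirement that the deficit be thought ischemic stays, so sudden deaths do not become strokes by default.
2. In limb (b), accept autopsy evidence of a relevant infarct, where available, alongside neuroimaging. Section 8.3 calls for autopsy only for deaths within 45 days of implant, so this will help in few later deaths.
3. As a supporting step in 18.2 and the CEC Charter, have the CEC check each death it already adjudicates against the amended definition, using the records available. A confirmed fatal ischemic stroke or systemic embolism counts as a primary effectiveness event at its onset date. A case that cannot be determined counts as an event only in a sensitivity analysis, to be added to SAP 8.10.

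If the Charter already has such a rule, Appendix I should state it or refer to it.

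The cost is a few words in Appendix I, one field on the CEC death form and one sensitivity analysis. Deaths already adjudicated would need a second look under the new wording, best done before unblinding. No visit, test or treatment changes. The event count may rise slightly.
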